## 7.0 SUBJECT ELIGIBILITY

### 7.1 Inclusion Criteria

1. Male and female patients
2. Diagnosis of the following tumor types
  - a. Non Hodgkin-Lymphoma, including:
    - i. Diffuse large B-cell lymphoma: Histopathologic confirmation
    - ii. Mantle cell lymphoma: Histopathologic confirmation
    - iii. Follicular lymphoma, all grades: Histopathologic confirmation
    - iv. Marginal zone lymphoma: Histopathologic confirmation
  - b. Chronic lymphocytic leukemia: Histopathologic or flow cytometric confirmation:
  - c. Multiple myeloma: Histopathologic or flow confirmation
3. Relapsed, refractory, or detectable disease after treatment with chimeric antigen receptor T-cells
  - a. Multiple Myeloma: patients must have exhausted all treatment options known to provide clinical benefit, and are refractory to a minimum of 3 prior lines of therapy (including an IMiD, PI, or anti-CD38 monoclonal antibody).
4. Have measurable disease, defined by histology:
  - a. Non-Hodgkin's Lymphoma, based on presence of lesions  $\geq 1.5$  cm that can be accurately measured in 2 dimensions by CT (preferred) or MRI, and are not included in any prior field of radiation therapy
  - b. Chronic lymphocytic leukemia: circulating lymphocytes  $\geq 5,000 / \text{mm}^3$
  - c. Multiple Myeloma, based on the International Myeloma Working Group (IMWG) criteria of having one or more of the following findings:
    - i. Serum M protein  $\geq 1.0 \text{ g/dL}$

- ii. Urine M protein  $\geq$  200 mg/24 hours
- iii. Involved serum free light chain level  $\geq$  10 mg/dL with abnormal  $\kappa/\lambda$  ratio
- iv. Measurable biopsy-proven plasmacytomas ( $\geq$  1 lesion has a single diameter  $\geq$  2 cm)
- v. Bone marrow plasma cells  $\geq$  30%
- 5. Age 18 years and older, and have the capacity to give informed consent
- 6. Anticipated survival of  $>$  3 months
- 7. ECOG performance status of 0-2 (See Appendix B)
- 8. Post CAR T cell receipt of intervening palliative radiation therapy is allowed
- 9. Adequate organ function, as defined by:
  - a. eGFR  $\geq$  20 ml/min
  - b. Alanine aminotransferase (ALT) and aspartate aminotransferase (AST)  $\leq$  3 x ULN and total bilirubin  $\leq$  2 x ULN
  - c. ANC  $\geq$  1,000/ $\mu$ L
  - d. Platelets  $\geq$  50,000/ $\mu$ L
  - e. Hemoglobin  $\geq$  8 g/dL

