### 9.4 Study Response Assessments

Safety assessment will occur through the study and consist of continuous surveillance and recording of adverse events (AEs) and serious adverse events (SAEs).

After the end of treatment, each subject will be followed for 30 days for adverse event monitoring (serious adverse events may be collected for 90 days after the end of treatment). Subjects may have post-treatment follow-up for disease status up to 5 years, or until disease progression, initiating a non-study cancer treatment, withdrawing consent, or becoming lost to follow-up.

4. Non-Hodgkin Lymphoma: PET-CT and CT (Diagnostic quality) after 2 cycles (8 weeks), then Diagnostic CT of chest, abdomen, and pelvis every 3 cycles (12 weeks) thereafter. Response assessment will be based on the Lugano Criteria
  - a. Initial response assessment after 2 cycles (8 weeks) with PET-CT and diagnostic CT
  - b. Diagnostic CT every 3 cycles thereafter
5. Chronic lymphocytic leukemia: PET-CT and CT (Diagnostic quality) after 2 cycles (8 weeks), then Diagnostic CT every 3 cycles (12 weeks) thereafter. A bone marrow aspirate +/- biopsy will be obtained at screening and to confirm CR. Response assessment based on IWCLL criteria
  - a. Initial response assessment after 2 cycles (8 weeks) with PET-CT and diagnostic CT
  - b. Diagnostic CT every 3 cycles (12 weeks) thereafter
6. Multiple myeloma: Assessment of serum protein electrophoresis (SPEP), serum free light chains (sFLC), every 4 weeks. 24-hour urine assessment of Bence-Jones Proteinuria only in subject who have this as sole marker of disease. Response assessment based on the IMWG. A bone marrow aspirate and biopsy will be obtained at screening and to confirm CR. PET-CT only to be performed for subjects with plasmacytoma as the only site of measurable disease at screening, after 2 cycles, then every 3 cycles (12 weeks) thereafter.

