Adverse events will be recorded from the time of a subject signing consent up until 30 days after the last dose of nivolumab, or 90 days after the last dose of nivolumab in the case of serious adverse events.

For subjects with multiple myeloma only.

The Sponsor-Investigator or sub-Investigator may waive screening bone marrow aspirate and biopsy requirements. For subjects with CLL/SLL and MM, repeat bone marrow biopsy only to be done after screening to confirm CR

Pregnancy test is only required in women of childbearing potential. Verbal report of pregnancy will be reported during conduct of the trial.

Tumor assessment imaging (see section 11.1.2.5) will be performed prior to cycle 3 (within 7 days of scheduled treatment dose) and every 3 cycles thereafter. Tumor assessment labs and/or imaging will also be performed as indicated per clinical standard of care (e.g. as appropriate for disease, to evaluate clinical suspicion of disease progression). Screening PET-CT and diagnostic CT done prior to screening up to day -42 may

be used for screening assessment. PET-CT and diagnostic CT will be performed at screening, then after 2 cycles on cycle 2 day 22. Thereafter, tumor assessment will comprise diagnostic CT of chest, abdomen, pelvis every 3 months. For multiple myeloma only, PET-CT should only be done amongst subjects in whom the only measurable disease is by imaging criteria – both at screening and for follow-up.

End of treatment evaluations should be done within 30 days (+/- 14 days) of the last dose of nivolumab or prior to the start of a new anti-cancer drug, whichever is first.

Correlative studies to include peripheral blood for storage for future biomarker analyses. Please see section 15 for details on blood collection and storage.

Long-term follow-up should be done according to the subject's physician standard of care. This may be performed at subjects' local physician's offices. Long-term follow-up will assess survival and disease progression. Subjects may be contacted by the study team until death, subject withdrawal of consent, lost to follow-up, or study termination, whichever occurs first.

If available, will be tested for PD-1 and PD-L1 IHC

The use of growth factors or transfusions to meet hematologic eligibility criteria is allowed

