## 19.5 APPENDIX E: Multiple Myeloma Definitions of Response and Progression (MODIFIED IMWG)

| Response Subcategory                                 | Response Criteria  |
|--|--|
| Stringent Complete Response (sCR)             | CR, as defined below, plus the following:
Normal FLC ratio b and absence of clonal cells c in bone marrow by immunohistochemistry or immunofluorescence.  |
| Complete Response (CR)b            | Negative immunofixation of serum and urine and disappearance of any soft tissue plasmacytomas, and < 5% plasma cells in bone marrow.   |
| Very Good Partial Response (VGPR)b | Serum and urine M-protein detectable by immunofixation but not on electrophoresis or ≥90% reduction in serum M-protein level plus urine M-protein level < 100 mg per 24 hour.  |
| Partial Response (PR)                         | ≥50% reduction of serum M-protein and reduction in 24-hour urinary M-protein by ≥ 90% or to < 200 mg per 24 hour. If serum and urine M-protein are unmeasurable, a ≥ 50% decrease in the difference between involved and uninvolved FLC levels is required in place of the M-protein criteria. In addition to the above criteria, if present at baseline, > 50% reduction in the size of soft tissue plasmacytomas is also required  |
| Minor (Minimal) Response (MR)                 | 25-49% reduction of serum M-protein and reduction in 24-hour urine M-protein by 50-89%, which still exceeds 200 mg per 24 hours. In addition, if present at baseline, 25-49% reduction in the size of soft tissue plasmacytomas is also required. No increase in the size or number of lytic bone lesions (development of compression fracture does not exclude response).   |
| Stable Disease (SD)                           | Not meeting criteria for CR, VGPR, PR, MR, or progression. Revised   |

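### Myeloma subjects can enter on plasmacytoma or marrow disease alone, but without usable M-protein or free light chains Appendix E gives them no route to partial response

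*Combined protocol and SAP*

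**What the plan says.** **Entry.** Section 7.1 item 4.c defines measurable myeloma by "criteria of having one or more of the following findings". Five findings follow. The fourth is "Measurable biopsy-proven plasmacytomas" (at least one lesion of 2 cm or more) and the fifth is "Bone marrow plasma cells" of at least 30%. Either is enough alone.

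**Assessment.** Section 9.4 requires SPEP and serum FLC every 4 weeks. It adds "PET-CT only to be performed for subjects with plasmacytoma as the only site of measurable disease", at screening, after 2 cycles and every 3 cycles after that. For marrow, Appendix A footnote 3 says "repeat bone marrow biopsy only to be done after screening to confirm CR".

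**Response.** Section 14.2 points to Appendix E, which is headed as a modified IMWG table. PR there requires a 50% or greater "reduction of serum M-protein and reduction in 24-hour urinary M-protein by" 90% or to below 200 mg per 24 hours. If M-protein is unmeasurable, a 50% or greater "decrease in the difference between involved and uninvolved FLC levels is required in place of the M-protein criteria". The PR entry ends: "In addition to the above criteria, if present at baseline, > 50% reduction in the size of soft tissue plasmacytomas is also required".

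**Denominator and decision rule.** Section 16.1 counts a subject as response evaluable after one response assessment. Section 16.4 stops for futility at 0 responses in 12 and rejects the null at 4 or more in 20.

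**The concern.** The entry rule accepts two kinds of disease that the response table cannot score as partly improved. For a plasmacytoma-only subject, the plan collects serial PET-CT but has no rule that turns shrinkage into PR. For a marrow-only subject, no marrow measurement short of CR confirmation is planned, and Appendix E has no marrow criterion for PR in any case.

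The table is also asymmetric. Progression can be declared from plasmacytoma growth or from marrow plasma cell percentage, so these subjects can fail on their marker but cannot partly respond on it. Footnote b adapts CR and VGPR for subjects measurable only by FLC, and nothing similar exists for the other two groups.

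With a threshold of 4 responses in 20, one response scored differently can decide the trial. The alternative to scoring a real partial response as failure is an ad hoc call by the investigator in an open-label study.

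**Working it through.** **1. Which response categories can be reached?** Take a subject with no usable serum or urine M-protein and no usable FLC.

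| Category (Appendix E) | Basis | Reachable? |
|---|---|---|
| CR | Negative immunofixation, plasmacytomas gone, marrow below 5% | Yes |
| VGPR | M-protein; FLC for FLC-only subjects | No |
| PR | M-protein, else FLC difference; plasmacytoma shrinkage in addition | No |
| MR | M-protein reduction; plasmacytoma shrinkage in addition | No |
| PD | Includes marrow percentage and plasmacytoma growth | Yes |

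The documents do not say which categories count in ORR. PR or better is assumed here. Counting MR would not help, because MR also needs an M-protein reduction.

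**2. The plan's own power.** From Section 16.4: n1 = 12, stop at 0 responses, N = 20, reject at 4 or more, rates of 6% and 26%.

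Power = Σ over x = 1 to 12 of P(Bin(12, 0.26) = x) × P(Bin(8, 0.26) ≥ 4 − x)

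- x = 1: 0.11369 × 0.34652 = 0.03939
- x = 2: 0.21969 × 0.65733 = 0.14441
- x = 3: 0.25729 × 0.91008 = 0.23416
- x ≥ 4: 0.38237 × 1 = 0.38237

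The sum is 0.8003, so the stated 80% reproduces. The same sum at 6% gives a type I error of 0.0286, inside the stated 0.05.

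**3. Power with k subjects who cannot be scored.** The k subjects fall at random among the 20, so the number j in stage 1 is hypergeometric. Stage 1 then has 12 − j scorable subjects and stage 2 has 8 − (k − j). Scorable subjects respond at 26% and the k at 0.

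For k = 1: with probability 12/20 the subject is in stage 1 (power 0.76331), and with probability 8/20 in stage 2 (power 0.76582). So 0.6 × 0.76331 + 0.4 × 0.76582 = 0.7643.

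**4. What a response route gives back.** The same calculation is repeated with the k subjects responding at rate q. Two values bracket the answer: q = 26% (the design alternative) and q = 4% (the nivolumab myeloma rate in Section 4.9, not from post-CAR-T subjects).

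| k | Power, none counted | Power, q = 4% | Gain (points) | Power, q = 26% | Gain (points) | Futility stop at 26%, none counted | Type I error at 6%, none counted |
|---|---|---|---|---|---|---|---|
| 0 | 0.8003 | – | – | 0.8003 | – | 0.027 | 0.0286 |
| 1 | 0.7643 | 0.7699 | 0.6 | 0.8003 | 3.6 | 0.033 | 0.0240 |
| 2 | 0.7234 | 0.7359 | 1.25 | 0.8003 | 7.7 | 0.039 | 0.0199 |
| 3 | 0.6774 | 0.6983 | 2.1 | 0.8003 | 12.3 | 0.048 | 0.0162 |

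The last column falls as k rises, so the gap is conservative for the test.

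**The case against.** A reader might infer that every subject who enters on plasmacytoma or marrow is a built-in non-responder unless CR is reached. The text does not support that. The FLC substitute in PR carries no measurability threshold; the 10 mg/dL cut-off belongs to eligibility. A subject with abnormal but sub-threshold FLC can formally reach PR through FLC, with plasmacytoma shrinkage added if present. A subject with trace M-protein can meet the first VGPR limb (visible on immunofixation, not on electrophoresis), possibly already at baseline. That is a poor route, but it is a formal one. The gap is limited to subjects with no usable marker.

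A reader might also infer a fixed loss of about 4 power points per subject. That holds only if these subjects would respond at 26%. Section 4.9 reports 4% and 0% for PD-1 monotherapy in myeloma. At 0% a route restores nothing, and the single response behind the 4% was a complete one, which Appendix E already counts.

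It can further be said that the published IMWG paper, cited as the source, may cover non-secretory disease. That cannot be checked here. Section 14.2 refers to Appendix E, whose heading says it is modified, so Appendix E is the natural operative text. The documents do not say which prevails.

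Finally, the affected group is a subset of one of three histologies, and the documents give no count or cap. This limits the size of the problem. It does not remove it, because Section 9.4 plans explicitly for plasmacytoma-only subjects.

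**Conclusion.** The point holds in limited form. Followed as written, Appendix E scores a real partial response as non-response when plasmacytoma or marrow is the only measurable disease and neither M-protein nor FLC is usable. Such a subject remains in the ORR denominator.

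With one to three such subjects and no response counted among them, power at 26% falls from 0.800 to between 0.764 and 0.677. The part that a response route would recover lies between 0.6 and 3.6 points for one subject and between 2.1 and 12.3 points for three, according to whether they respond at 4% or 26%. These figures assume random order of accrual, 26% in everyone else and no CR in the affected group when no route exists. The number of such subjects is also assumed. The effect is a lower ORR and lower power, with no inflation of type I error. It should be corrected, but it does not undermine the design.

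**What to change.** **Plasmacytoma-only disease.** Add one rule to Appendix E: where plasmacytoma is the only measurable disease and M-protein and FLC are not usable, PR is the existing reduction of more than 50% in plasmacytoma size, taken alone and read from the PET-CT in Section 9.4. The rule should state:

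- the size measure (a diameter or a product of diameters);
- how footnote a's requirement for two consecutive assessments applies. With scans at 8 weeks and every 12 weeks after that, the first such pair falls at weeks 8 and 20 (8 + 12);
- that footnote a's waiver of radiographic studies does not apply to these subjects.

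Section 10.5 lists no PET-CT for myeloma from cycle 7 and should be aligned with Section 9.4.

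**Marrow-only disease.** Reconcile Section 7.1 item 4.c.v with Appendix E and the marrow schedule, since no marrow measurement short of CR confirmation is planned. Whether to change the entry rule, the criteria or the schedule is a trade-off for the sponsor.

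**ORR definition.** State which response categories count.

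The cost is a short edit to the criteria, made before response data are reviewed, with no new scans beyond those in Section 9.4. The downside is that PR in these few subjects would rest on imaging alone.

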## 7.2 Exclusion Criteria

- 1. Receipt of intervening systemic therapy after CAR T-cell infusion
- 2. History of another primary malignancy that has not been in remission for at least 1 year (with the exception of non-melanoma skin cancer, curatively treated localized prostate cancer, curatively treated superficial bladder cancer and cervical carcinoma in site on biopsy or a squamous intraepithelial lesion on PAP smear)
- 3. Active hepatitis B, hepatitis C at time of screening
- 4. Known (HIV) seropositivity
- 5. Subjects with uncontrolled infection
- 6. Concurrent use of other anticancer agents or experimental treatments
- 7. Active autoimmune disease requiring immunosuppressive therapy with the exception of vitiligo and autoimmune alopecia
- 8. Known active CNS involvement
- 9. Subjects with a condition requiring systemic treatment with either corticosteroids ( $>$ 10 mg daily prednisone equivalent) or other immunosuppressive medications within 14 days of study drug administration. Inhaled or topical steroids, and adrenal replacement doses are permitted in absence of active autoimmune disease
- 10. Known history of any active infectious pneumonitis
- 11. Presence of acute or chronic graft-versus-host disease (GVHD) requiring active treatment unless limited to skin involvement and managed with topical steroid therapy alone
- 12. Has active cytokine release syndrome
- 13. Pregnancy or breastfeeding: Women of childbearing potential (WOCBP) must have a negative serum or urine pregnancy test (urine pregnancy test: minimum sensitivity 25 IU/L or equivalent units of human chorionic gonadotropin [hCG]) within 14 days of the first dose of study drug.

Women must not be breastfeeding. Females of nonchildbearing potential are those who are postmenopausal greater than 1 year or who have had a bilateral tubal ligation or hysterectomy. Females of childbearing potential and males who have partners of childbearing potential must agree to use 2 effective contraceptive methods during the study and for 8months following the last dose of nivolumab.

### **7.3 Criteria for Removal/Withdrawal from Treatment**

Subjects may be removed from this study at any time at their discretion. Subjects may also be removed from this protocol if they develop any untoward side effects from the study medications. In addition, there are stopping rules in place for lack of efficacy and excessive toxicity as detailed in the statistical section.

If a subject withdraws consent to participate in the study or aspects of the study, attempts should be made to obtain permission to record survival data up to the protocol-described end of the subject follow-up period. Survival data are important to the integrity of the final study analysis. Documentation in the medical record should state that the subject is withdrawing from the study and what, if any, selected data the subject will permit the investigator to obtain.

### **7.4 Patient Evaluation and Counseling**

Patients will be seen at the Fred Hutchinson Cancer Center (FHCC) for consideration of treatment options for their disease. The protocol will be discussed thoroughly with the patient and other family members if appropriate, and all known and potential risks to the patient will be described. The procedure and alternative forms of therapy will be presented as objectively as possible, and the risks and hazards of the procedure explained to the patient. Signed consent will be obtained from the patient using forms approved by the FHCRC IRB. The consent form describes the purpose of the study, the procedures to be followed, and the risks and benefits of participation.

## **8.0 SUBJECT REGISTRATION**

Subjects will be registered by the Study Coordinator and entered into the Clinical Trial Management System (CTMS), OnCore. A complete, signed, study consent and HIPAA authorization, in addition to a completed eligibility checklist signed by the PI or authorized sub-investigator are required for registration.

## **9.0 STUDY INTERVENTIONS**

[figure not shown]
This is a single arm, unblinded phase II trial of nivolumab, a PD-1 inhibitor, for treatment of patients with hematologic malignancies (including B-cell non-Hodgkin lymphoma, chronic lymphocytic leukemia, and multiple myeloma) who either experience relapse or have persistent disease after treated with CAR T-cell therapy.

Approximately 20 subjects will be enrolled on this study, which will include a screening phase, an active treatment phase, and a follow-up phase. Before any study-related procedure can be performed, all

subjects must sign an informed consent form (ICF). Subjects will be evaluated for eligibility at screening.

The active treatment phase will extend from cycle 1, day 1, until study treatment discontinuation due to disease progression, initiation of subsequent anti-cancer therapy, unacceptable toxicity, withdrawal, or completion of study treatment. A study schema is depicted in figure 1.

### Figure 1. Study Design

The study will be conducted as a single arm phase II trial. After 2 cycles, an interim response assessment will be conducted to evaluate for early progression. Subjects with disease progression at that assessment will be discontinued from study treatment. Subjects will undergo disease-specific monitoring for response, as outlined in Section 9.5, during treatment on study.

### 9.1 Administration of Nivolumab

For treatment related questions, please contact [name] at [contact].

Nivolumab will be administered as a 30-minute IV infusion on Day 1 of each 28-day cycle.

The nivolumab dose is fixed at 480 mg. Doses of nivolumab may be interrupted, delayed, or discontinued depending on how well the participant tolerates the treatment. Refer to section 4.0 for further information on administration.

Management and dose delays associated with nivolumab AEs can be managed by referring to Section 4.8, or Section 9.5.

### 9.2 Concomitant Medication and Supportive Care Guidelines

Medications used during the course of the clinical trial should be documented.

#### **Prohibited Concomitant Therapy During Active Study Treatment**

- The administration of concurrent medications intended to treat the primary cancer is not allowed during protocol therapy. This includes chemotherapy, investigational agent, biologic agent, or other anti-tumor agents. Radiation therapy is also prohibited
- Immunosuppressive agents (except to treat a drug-related adverse event)

- Topical and inhaled corticosteroids to treat other medical conditions are allowed. Immunosuppressive doses of corticosteroids are not permitted ( $> 10$  mg daily prednisone or equivalent), except to treat a drug-related adverse event or for treatment of adrenal insufficiency. Intermittent corticosteroid usage to treat infusion reactions is allowed

Subjects should be discouraged from taking any alternative or naturopathic medications since these agents may interact with study therapy. Any use of these medications should be at the judgment of the treating physician and documented in the subject's medical record.

